9.1.5 Prior and Concomitant Medication Review

Medications are defined as prescription and over-the-counter drugs, vitamin supplements, nutraceuticals, and oral herbal preparations. Qualified site personnel are to review subject medication use.

9.1.6 Physical Examinations

Qualified site personnel will conduct physical examinations.

9.1.7 Vital Sign Measurements

Body temperature will be measured with an oral (temperature taken at floor of the mouth) or tympanic thermometer. The same method (eg, oral or tympanic) must be used for all subsequent measurements for each individual subject and should be the same for all subjects.

Subjects should rest in a semirecumbent position for at least 5 minutes before having vital sign measurements obtained. Vital signs will include HR, systolic blood pressure, and diastolic blood pressure. The same method (eg, same and appropriately sized cuff, manual, or automated) must be used for all measurements for each individual subject and should be the same for all subjects.

Subjects will continue to rest in a semirecumbent position from the time of dosing until 4 hours postdose except to stand for the measurement of standing vital signs (if needed) or other trial-related procedure.

9.1.8 Height and Weight

Body weight and height will be obtained with the subject's shoes off and jacket or coat removed.

9.1.9 BMI

BMI equals a person's weight in kilograms divided by height in meters squared ($BMI=kg/m^2$). Body weight and height will be obtained with the subject's shoes off and jacket or coat removed.

BMI will be rounded to the nearest whole number according to the standard convention of 0.1 to 0.4 round down and 0.5 to 0.9 round up.

9.1.10 12-Lead ECG

Special care must be taken for proper lead placement by qualified personnel. Skin should be clean and dry before lead placement. Subjects may need to be shaved to ensure proper lead placement. Female subjects may need to remove their bras.

Subjects should be resting in a semirecumbent position for at least 5 minutes before each ECG measurement.

QT intervals with Fridericia correction method (QTcF) will be used to calculate QT intervals in this trial.

Before each trial period, a predose ECG will be obtained within approximately 30 minutes before dosing. This measurement will be used as the baseline. The principal investigator should arrange to have a trial cardiologist available as needed to review ECG tracings with abnormalities.

If a subject demonstrates an increase in QTcF interval ≥ 40 msec compared with a predose baseline measurement, the ECG will be repeated within 5 minutes. The average value of the QTcF interval from the 2 ECGs will represent the value at that time point. If the average QTcF interval increase from Baseline for any postdose time point is ≥ 40 msec, the subject will continue to be monitored by repeat 12-lead ECGs every 60 minutes for at least 4 hours or until the QTcF is within 40 msec of the baseline value. If prolongation of the QTcF interval ≥ 40 msec persists, a consultation with a trial cardiologist may be appropriate and the sponsor should be notified.

If the QTcF interval is ≥ 500 msec, the sponsor should be notified and the ECGs should be reviewed by a cardiologist. The subject should be telemetry-monitored (until the QTcF is < 500 msec) or should be considered for transfer to a location where closer monitoring is available.

If the subject has unstable hemodynamics, or has any clinically significant dysrhythmias noted on telemetry, the subject should be immediately transferred to an acute care setting for definitive therapy.

If repeat ECGs are required, the clinical site will decide whether to leave the electrodes in place or mark the position of the electrodes for subsequent ECGs. To mark the position of the electrodes, 12-lead electrode sites will be marked on the skin of each subject with an ECG skin marker pen to ensure reproducible electrode placement.

The following ECG parameters will be recorded: HR, PR-interval, QRS-duration, QT-interval, QTcF-interval, and the interpretation of the ECG profile by the principal investigator.

9.1.11 AE Monitoring

AE monitoring begins after signing of informed consent. Changes in subject health status from baseline assessment to trial drug administration should be captured in the subject's medical history. A complete description of AE collections and procedures is provided in Section 10.0.

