10.0 ADVERSE EVENTS

10.1 Definitions and Elements of AEs

An AE is defined as any untoward medical occurrence in a clinical investigation subject who has signed informed consent to participate in a trial; it does not necessarily have to have a causal relationship with the treatment.

An AE can therefore be any unfavorable and unintended sign (eg, a clinically significant abnormal laboratory finding), symptom, or disease temporally associated with the use of a drug, whether or not it is considered related to the drug.

An untoward finding generally may:

- Indicate a new diagnosis or unexpected worsening of a preexisting condition. (Intermittent events for pre-existing conditions underlying disease should not be considered AEs.)
- Necessitate therapeutic intervention.
- Require an invasive diagnostic procedure.
- Require discontinuation or a change in dose of trial medication or a concomitant medication.
- Be considered unfavorable by the investigator for any reason.

Diagnoses versus signs and symptoms:

- Each event should be recorded to represent a single diagnosis. Accompanying signs (including abnormal laboratory values or ECG findings) or symptoms should NOT be recorded as additional AEs. If a diagnosis is unknown, sign(s) or symptom(s) should be recorded appropriately as an AE(s).

Laboratory values and ECG findings:

- Changes in laboratory values or ECG parameters maybe considered to be AEs if they are judged to be clinically significant (ie, if some action or intervention is required or if the investigator judges the change to be beyond the range of normal physiologic fluctuation). A laboratory re-test and/or continued monitoring of an abnormal value are not considered an intervention. In addition, repeated or additional noninvasive testing for verification, evaluation, or monitoring of an abnormality is not considered an intervention.
- If abnormal laboratory values or ECG findings are the result of pathology for which there is an overall diagnosis (eg, increased creatinine in renal failure), the diagnosis only should be reported appropriately as an AE.

Pre-existing conditions:

- A pre-existing condition (present at the time of signing of informed consent) is considered a concurrent medical history condition and should NOT be recorded as an AE. A baseline evaluation (eg, laboratory test, ECG, x-ray) should NOT be recorded as an AE unless related to a trial procedure. However, if the subject experiences a worsening or complication of such a

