10.2.9 Collection and Reporting of AEs, SAEs, and Abnormal LFTs

10.2.9.1 Collection Period

Collection of AEs (ie, AEs, SAEs, and abnormal LFTs) will commence at the time the subject signs the informed consent. Routine collection of AEs will continue until the Follow-up Visit 10-14 days after the last dose of trial drug. For subjects who discontinue before the administration of trial medication, AEs will be followed until the subject discontinues trial participation.

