7.5 Medical History and Concurrent Medical Conditions

Medical history is defined as significant conditions or diseases that resolved at or prior to the time of informed consent. Concurrent medical conditions are defined as significant conditions or diseases that are present at signing of informed consent.

Medical history and concurrent medical conditions will be coded using the MedDRA coding system.

Medical history and concurrent medical conditions will be listed by site and subject number.

There will be no summary or inferential analysis of medical history and concurrent medical conditions.

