7.11.1 Adverse Events

A treatment -emergent adverse event (TEAE) will be defined as an AE or serious adverse event (SAE) that started or worsened after first study drug administration and within 30 days of last dose of study drug (onset date – date of last dose + 1 ≤ 30). A TEAE will be attributed to a regimen if the TEAE occurs after administration of the study drug in a period and up to just prior to study drug administration in the next period. A TEAE that occurs after administration of the study drug in the last period and up to 30 days after the last study drug dose is attributed to the regimen received in the last period. All AE verbatim terms will be coded by system organ class (SOC) and preferred term using (PT) the MedDRA coding system.

TEAEs will be summarized by regimen (TAK-954 alone, itraconazole alone, and TAK-954 with itraconazole) and overall. The tables will include the number and percentage (N [%]) of subjects reporting any event for that term. The following TEAE tables will be summarized.

- Overview of TEAEs.
- TEAEs by SOC and PT at subject and event level.
- Subject Mappings for TEAEs.
- TEAEs by PT.
- Relationship of TEAEs to Study Drug by SOC and PT.
- Drug-Related TEAEs by SOC and PT.
- Severity of TEAEs by SOC and PT.
- Severity of Drug-Related TEAEs by SOC and PT.

In addition, pretreatment events (PTEs) will be summarized overall by SOC and PT.

For each regimen and overall, subjects reporting more than one occurrence for a term (SOC or PT) being summarized will be counted only once using the most extreme incident (most severe for the severity tables and related for the relationship to study drug tables).

Data listings will be provided for all TEAEs, PTEs, TEAEs that led to study discontinuation, TEAEs that led to abnormal liver functions, SAEs, AEs that resulted in death, and AEs occurring more than 30 days after the last dose of study medication.

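### Protocol 9.1.11 sends health changes before dosing to medical history, contradicting the AE rules in Protocol Section 10 and SAP 7.5; if sites follow it, the pretreatment event outputs may be incomplete

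*Protocol*

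**What the plan says.** Protocol 9.1.11 is three sentences long. It opens with "AE monitoring begins after signing of informed consent". It then gives the rule at issue: "Changes in subject health status from baseline assessment to trial drug administration should be captured in the subject's medical history". It closes with a pointer: "A complete description of AE collections and procedures is provided in Section 10.0". The starting point of the rule, the baseline assessment, is not defined there or elsewhere for this purpose.

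Protocol Section 10 dates everything from consent. Section 10.1 defines an AE as "any untoward medical occurrence in a clinical investigation subject who has signed informed consent to participate in a trial", with no condition that a dose has been given. The same section sets the boundary of medical history: "A pre-existing condition (present at the time of signing of informed consent) is considered a concurrent medical history condition". Section 10.2.9.1 says that collection of AEs "will commence at the time the subject signs the informed consent". Section 10.2.9.2 puts all AEs on the AE page of the eCRF, with severity, causality, relationship to trial procedures and outcome.

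The SAP draws the same line. Section 7.5 states: "Medical history is defined as significant conditions or diseases that resolved at or prior to the time of informed consent". It defines concurrent conditions as those present when consent is signed, and it lists both categories without summarizing either. Section 7.11.1 says that "pretreatment events (PTEs) will be summarized overall by SOC and PT", and also plans a listing of these events.

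**The concern.** A subject who develops a nonserious condition after consent and before the first infusion falls under two instructions. Section 9.1.11 points to the medical history form and Section 10 points to the AE page. Neither section says which prevails.

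If the event is entered only as medical history, the fields that 10.2.9.2 requires are not assured. Relationship to trial procedures matters most here, because Screening and Day -1 procedures take place before any drug is given. The event would also be missing from the pretreatment event table and listing. It would appear instead in a medical history listing whose own SAP definition excludes it. At stake is the completeness of safety reporting before dosing.

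**Working it through.** No alpha, power, SD or rate is involved, so the check is a comparison of the texts. Take one test case: a nonserious condition that starts after consent and before the first dose of TAK-954 on Day 1 of Period 1.

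| Source | Where the test case goes |
|---|---|
| Protocol 9.1.11 | Medical history, if it falls after the undefined baseline assessment |
| Protocol 10.1, AE definition | AE, because consent has been signed |
| Protocol 10.1, pre-existing conditions | Not medical history, because it was not present at consent; worsening after consent of a condition that was present is also an AE |
| Protocol 10.2.9.1 | Inside the AE collection period |
| Protocol 10.2.9.2 | AE page; nonserious events before first exposure are still called AEs, and only their follow-up is waived |
| SAP 7.5 | Neither medical history (not resolved by consent) nor a concurrent condition (not present at consent) |
| SAP 7.11.1 | Pretreatment event, by the plain meaning of the term |

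Only 9.1.11 sends the case to medical history. Every other passage either makes it an AE or excludes it from medical history.

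**Length of the window.** The Schedule of Trial Procedures places Screening, with consent, on Days -28 to -2, and the first dose is on Day 1. SAP 7.1.2 has no Day 0. Consent on Day -28 therefore gives 28 days before dosing, and consent on Day -2 gives 2 days. Because 9.1.11 runs from the baseline assessment and not from consent, 28 days is an upper bound. If the term meant the Day -1 check-in, the window would be 1 day.

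**Which outputs are touched.**
- The pretreatment event table and listing draw on events before dosing, so they depend on where such events are recorded.
- TEAEs are defined in SAP 7.11.1 by onset or worsening after first study drug administration. The test case is not a TEAE under either filing, and Protocol 10.1 requires later worsening to be recorded as an AE.
- Serious events before dosing follow the normal SAE procedure under Protocol 10.2.9.3.
- The primary endpoints, Cmax and AUC∞, use plasma concentrations only.

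**Number of events.** It cannot be derived. The documents give no rate of pretreatment events.

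**A related gap.** The SAP does not define pretreatment event. Section 7.1.1 says there are no study-specific definitions, and the abbreviation list omits the term. That it covers all AEs from consent to first dose is an inference, though the natural one.

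**The case against.** The strongest reply is that 9.1.11 diverts nothing. It starts AE monitoring at consent, does not tell the site to withhold an AE entry, and defers to Section 10 for the full procedure. A site could note the change in medical history and also complete an AE page. Section 10.2.9.2 plainly expects nonserious AEs before dosing, and the planned pretreatment event outputs show that the sponsor expects the data.

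Much of this stands. Loss of events is conditional on a site acting on 9.1.11 alone, and it would be wrong to call it certain. The pointer does not remove the conflict, however, because Section 10 is the text that the sentence contradicts. Section 9.0 also presents these subsections as the description of procedures and data to be collected, so a site may reasonably act on them. Even double entry would put an event into medical history that SAP 7.5 excludes from it.

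It would also be too broad to say that every event after consent is an AE. Section 10.1 has exceptions, among them baseline evaluations unrelated to a trial procedure, preplanned procedures, and expected episodic or degenerative changes.

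A reader might infer something stronger: that baseline is taken anew in each period, so the sentence could divert events during the itraconazole days before the Day 4 infusion and distort the TEAE comparison between regimens. The documents do not support this.
- The period baselines in the Trial Summary and in Protocol 9.1.10 concern laboratory, ECG and vital-sign values, not health status.
- Medical history is scheduled only at Screening, so Period 2 has no such collection into which events could be diverted.
- Protocol 9.5 treats Period 2 Day 1, when itraconazole starts, as a day of trial drug administration, so a window for that period would close before any itraconazole exposure.
- Pretreatment events are summarized overall and not by regimen, so misfiling them cannot bias a comparison of regimens.

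**Conclusion.** The contradiction is real but its reach is small. Protocol 9.1.11 states a recording rule that conflicts with Protocol 10.1, 10.2.9.1 and 10.2.9.2 and with SAP 7.5. If a site follows it in preference to Section 10, nonserious events between consent and first dose may be filed only as medical history, and the SAP 7.11.1 pretreatment event table and listing would then be incomplete.

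The conclusion rests on two assumptions: that at least one site user reads 9.1.11 as the operative instruction, and that pretreatment event in the SAP means an AE with onset from consent to first dose. It is a minor matter, worth correcting because the correction is simple.

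**What to change.** In Protocol 9.1.11, replace the sentence on health changes with a rule that agrees with Section 10:

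- New or worsened conditions from signing of consent to the first dose of trial drug are recorded on the AE page, subject to the exceptions in 10.1, and are reported as pretreatment events.
- Medical history holds only conditions present at consent or resolved by then.

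This removes the undefined baseline assessment from the rule. In the SAP, define a pretreatment event in 7.1.1 or 7.11.1 as an AE with onset or worsening after consent and before the first dose, so that the table and listing have a stated scope. Align the CRF completion guidance with both.

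The cost is one protocol sentence, one SAP definition, a line of CRF guidance, and a few more AE pages for the site.

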9.2 Laboratory Procedures and Assessments

Laboratory samples will be collected in accordance with acceptable laboratory procedures. Samples will be taken after a minimum 8-hour overnight fast on the days stipulated in the Schedule of Trial Procedures (Section 3.0).

9.2.1.1 Clinical Laboratory Tests

Chemistry

Chemistry evaluations will consist of the following standard chemistry panel:

Albumin	Alkaline phosphatase
ALT	AST
Blood urea nitrogen	Calcium
Bicarbonate	Chloride
Creatinine	Glucose
Gamma-glutamyl transferase	Sodium
Potassium	Bilirubin (total), if above ULN, will be fractionated
Protein (total)	

Hematology

Hematology will consist of the following tests:

Erythrocytes (red blood cells [RBCs])	Hemoglobin
Hematocrit	Platelets
Leukocytes (white blood cells [WBCs]) with absolute differential	

Urinalysis

Urinalysis will consist of the following tests:

Protein	Glucose
Blood	Nitrite

Urine microscopy will be performed if urinalysis is abnormal. Microscopy consists of RBC/high-power field, WBC/high-power field, and casts.

Urine Drug Screen

A urine drug screen will include the following tests:

Amphetamines	3,4-methylenedioxy-methamphetamine (MDMA)
Barbiturates	Methadone/metabolite
Benzodiazepines	Opiates
Buprenorphine/metabolite	Oxycodone/oxymorphone
Cannabinoids	Phencyclidine
Cocaine/metabolites	

Alcohol Screen

Subjects will undergo a urine alcohol test. An alcohol breath test may be performed at the discretion of the investigator.

9.2.1.2 Screening

Serum

Serum evaluations will include the following tests:

HIV test	FSH (females only)
	Hepatitis panel, including HBsAg and anti-HCV

9.3 PK and PGx Samples

A portion of the DNA sample will be analyzed for the presence of allelic variants in drug metabolizing enzymes, drug transporters, or putative drug targets that may contribute to the variability in the PK of TAK-954 (Drug Metabolism Enzymes and Transporters).

As PGx is an evolving science, many genes and their functions are not yet fully understood. Future data may suggest a role of these genes in drug response, which may lead to additional hypothesis-generating exploratory research and diagnostic development on stored samples.

Samples for PK analysis will be collected as specified in the Schedule of Trial Procedures (Section 3.0). Please refer to the Laboratory Manual for information on the collection, processing, and shipment of samples to the central laboratory.

It is anticipated that the total blood volume drawn for the trial will be approximately 300 mL.

Primary specimen collection parameters are provided in [Table 9.a](#).

Table 9.a Primary Specimen Collections

Specimen Name	Primary Specimen	Primary Specimen Derivative	Description of Intended Use	Sample Collection
Plasma sample for TAK-954 PK	Plasma		PK measurements	Mandatory
Urine sample for TAK-954 PK	Urine		PK measurements	Mandatory
Blood sample for DNA PGx	Blood	DNA	PGx measurements	Mandatory
Blood sample for RNA PGx	Blood	RNA	PGx measurements	Mandatory

9.3.1 PK Evaluations

The PK parameters of TAK-954 will be derived using noncompartmental analysis methods and will be determined from the concentration-time data for all evaluable subjects. Actual sampling times, rather than scheduled sampling times, will be used in all PK computations involving sampling times. A more detailed description will be given in the clinical pharmacology analysis plan.

The following plasma PK parameters for TAK-954 will be calculated on Day 1 of Trial Period 1 and Day 4 of Trial Period 2:

- C_{\max}
- AUC_{∞}
- $t_{1/2}$

Other PK parameters may be calculated if deemed necessary for the interpretation of the data. All efforts will be made to obtain the PK samples at the exact nominal time relative to dosing. However, samples obtained within 10% of the nominal time from dosing will not be captured as a

protocol deviation, as long as the exact date and time of the dosing and sample collection is noted on eCRF.

CCI

9.3.2 PGx Measurements

9.3.2.1 Blood Sample for DNA and RNA PGx Measurements

When sampling of whole blood for PGx analysis occurs, every subject must sign an informed consent/be consented in order to participate in the trial. PGx is a component of the trial; participation is mandatory.

PGx is the study of variations of DNA and RNA characteristics as related to drug response. There is increasing evidence that an individual's genetic background may impact the PK (absorption, distribution, metabolism, and excretion), pharmacodynamics (pharmacologic effects), and/or the clinical outcome (efficacy and/or safety).

PGx research in this trial may be conducted to understand how individual genetic variation in subjects impacts their trial drug treatment response. This information may be also be used, for example, to develop a better understanding of the safety and efficacy of TAK-954 and other trial drugs, to increase understanding of the disease/condition being studied and other related conditions, gain a better understanding of the drug pharmacology and for generating information needed for research, development, and regulatory approval of tests to predict response to TAK-954.

Whole blood samples for DNA and RNA isolation will be collected from each consented subject in the trial. If necessary and feasible, a second aliquot of blood may be taken at a later time point if isolation of DNA from the first sample was not successful or possible.

Since PGx is an evolving science, many genes and their functions are not yet fully understood. Future data may suggest a role of these genes in drug response, which may lead to additional hypothesis-generating exploratory research and diagnostic development on stored samples.

Detailed instructions for the handling and shipping of samples are provided in the Laboratory Manual.

